1.2 PROPOSED MECHANISM OF ACTION

Nonclinical studies have shown sandalwood oil to have anti-inflammatory, anti-proliferative, anti-carcinogenic, anti-fungal, anti-viral and bactericidal activities. Ongoing programs are focused on the evaluation and/or development of assays to assess the activity of SAN007 against various inflammatory markers, as well as analyze its anti-proliferative activity to supplement the clinical programs. EISO has shown specific anti-proliferative cytotoxicity against UV and oncogenically transformed cell lines while leaving normally dividing cells unaffected at the same doses. Sandalwood oils have been shown to mimic ibuprofen non-steroidal anti-inflammatory drugs that act by inhibiting cyclooxygenases suggesting a possible

mechanism for the observed anti-inflammatory properties of topically applied sandalwood oils and providing a rationale for use in products requiring anti-inflammatory effects [Ref Sharma 2014].

2. OBJECTIVES

The objectives of this trial are:

- To evaluate the safety of SAN007 when administered to subjects with mild to moderate atopic dermatitis.
- To evaluate the tolerability of SAN007 when administered to subjects with mild to moderate atopic dermatitis.
- To evaluate the preliminary efficacy of SAN007 when administered to subjects with mild to moderate atopic dermatitis.

3. STUDY PLAN

3.1 OVERALL STUDY DESIGN

This trial will be a double-blind, randomized, placebo-controlled, safety, tolerability and efficacy trial of SAN007 treatment regimen when administered daily for up to 28 days to subjects at least 18 years of age, with atopic dermatitis.

Subjects will enter the Screening Period once the informed consent and photographic consent process has been completed. Subjects with a total body surface area (BSA) of \geq 2% and \leq 15% atopic dermatitis involvement, in the treatable areas, and who meet all of the inclusion, and none of the exclusion criteria, will be enrolled.

Once subject eligibility is confirmed and the screening procedures completed, the subject will start the Treatment Period of the study. All enrolled subjects will receive either 5% SAN007 or placebo cream (randomized in a 2:1 ratio) OR 10% SAN007 or placebo cream (randomized in a 2:1 ratio) with the first dose applied at Visit 1 Baseline. Subjects will be instructed on how to apply the study medication twice daily, ≥8 hours between application, for 28 days. Subjects will return to the clinic on Study Days 7,14, and 28 for study-related assessments. Subjects will receive a telephone contact from the site, on Study Days 21 and 35.

Safety will be assessed by evaluating adverse events (AEs) with respect to severity, duration, and relationship to study drug.

In addition, cutaneous tolerability will be evaluated at each visit. Tolerability evaluation will be based on subjects reporting discomfort during or immediately following application of SAN007. This will also be recorded as an AE. The study exclusion areas are not to be used in this evaluation.

Efficacy will be assessed at each study visit through the completion of the IGA, EASI, and BSA calculation.

During the active treatment period, Subjects will return to the study site, according to the study schedule, for interim assessments and recording of concomitant medication(s) and adverse events (AEs).

Figure 4-1 Study Design

Screening	Baseline	+	← Treatment →			Follow-Up	
Day -7 to	Day 1	Day 7 (±2 days)	Day 14 (±2 days)	Day 21 (±2 days)	Day 28 (±2 days)	Day 35 (±2 days)	
o diw s	Visit 1	Visit 2	Visit 3	Visit 4 (Telephone Call)	Visit 5	(Telephone Call)	

3.2 STUDY ENDPOINTS

The primary purpose of this study is to determine the safety profile of SAN007. Safety will be assessed by evaluating adverse events (AEs) with respect to severity, duration, and relationship to study drug.

Tolerability will be based on the number of subjects reporting discomfort during, or immediately, following application of SAN007. This will also be recorded as an AE. The study exclusion areas are not to be used in this evaluation.

Preliminary Efficacy will be evaluated using the following:

- The preliminary efficacy endpoint will be the percentage of subjects who have a
 ≥ 25% reduction in the Eczema Area and Severity Index (EASI) score at any point
 during the trial.
- Number of subjects achieving an Investigator Global Assessment (IGA) of "clear" or "almost clear" at any time point during the 28 days of therapy.
- Percentage of subjects who have a ≥50% reduction in the Eczema Area Severity Index (EASI) score at any point during the trial.
- Percentage of subjects achieving at least a 1-grade improvement in IGA score

 Percentage of subjects who have at least a 20% reduction in BSA affected by atopic dermatitis

Additional secondary and exploratory endpoints may be outlined in the statistical analysis plan.

3.3 DISCUSSION OF DESIGN

This Phase 2 study is designed to determine the safety profile of SAN007. In addition, the study may potentially provide estimates of improvement rates resulting from the topical application of SAN007. Based on the safety profile of EISO in this population and improvement rates, it is anticipated that confirmatory Phase 3 studies with appropriate sample sizes can be developed.

4. SELECTION OF STUDY POPULATION

4.1 NUMBER OF SUBJECTS REQUIRED

Up to 100 subjects, from the time of this amendment, at least 18 years of age, with a diagnosis of mild to moderate atopic dermatitis will be enrolled in this study to ensure up to 90 subjects complete the study.

4.2 INCLUSION CRITERIA

Subjects will be included in the trial if they meet all the following criteria:

- 1. Are at least 18 years of age.
- 2. Have atopic dermatitis, as determined by an EASI score of ≥2 and ≤50 (Hanifin, 2001).
- 3. Total body surface area (BSA) of atopic dermatitis involvement ≥2% and ≤15%, excluding restricted treatment areas from the calculation.
- 4. Have atopic dermatitis that has been clinically stable for ≥ 1 month prior to the Screening Visit.
- 5. Are able to obtain written informed consent in a manner approved by the Institutional Review Board and comply with the requirements of the study.
- 6. Are willing to refrain from using any lotions, moisturizer, cleansers, cosmetics or creams, other than those issued as part of the study, on the target treatment areas during the treatment period.
- 7. Are free of any systemic or dermatologic disorder, which, in the opinion of the investigator, would interfere with the study results or increase the risk of adverse events.

- 8. Are willing to refrain from exposure to artificial ultraviolet radiation for the duration of the study.
- 9. Are willing to cover target treatment areas to avoid exposure to natural ultraviolet radiation for the duration of the study.
- 10. If female of childbearing potential, must be willing to practice an acceptable form of birth control for the duration of the study. i.e. oral contraceptive, barrier method or intrauterine device.
- 11. Are willing to avoid participation in any other clinical trial for the duration of this study.
- 12. Are willing to refrain from treating restricted areas, which will be excluded from IGA assessments and BSA calculation. These areas are as follows: head, neck, soles of feet, palms of hands, axillae, or intertriginous areas.

4.3 EXCLUSION CRITERIA

Subjects will be excluded from the trial if they meet any of the following criteria:

- 1. Have a sibling or immediate family member already participating in this trial.
- 2. Currently requires and/or, in the past month, has required topical use of a medium or high potency steroid.
- 3. Atopic dermatitis that, in the opinion of the investigator, is likely to stem from an allergic reaction. (i.e. contact dermatitis)
- 4. Have <2% or >15% total BSA of atopic dermatitis involvement.
- 5. Have participated in any interventional clinical trial in the previous 30 days to the screening visit.
- 6. Have a known sensitivity to any of the constituents of the test product including sensitivities to sandalwood oil, fragrances or any member of the Compositae family of vascular plants (e.g., sunflowers, daisies, dahlias, etc.).
- 7. Have received phototherapy within the last two months prior to enrollment.
- Have received any systemic medication for atopic dermatitis in the past two
 months that would interfere with the evaluation of atopic dermatitis
 (excluding antihistamines or leukotriene inhibitors).
- 9. Have a present condition or abnormality that, in the opinion of the Investigator, would compromise the safety of the subject or the quality of the data.
- Are pregnant, breast-feeding or plan to become pregnant at any point for the duration of the trial.

- 11. Are not willing to practice an approved form of birth control while on the study drug for the duration of the trial. i.e. oral contraceptive, barrier method or intrauterine device.
- 12. Have been treated, with prescription medication for atopic dermatitis, within 60 days prior to the Baseline visit.
- 13. Have any evidence of systemic cancer, squamous cell carcinoma, basal cell carcinoma, in the last 5 years or any other confounding skin condition.
- 14. Have undergone treatments with topical atopic dermatitis drug products, other than retinoids or corticosteroids, within 14 days prior to the Baseline Visit, and for therapy containing corticosteroids or retinoids within 28 days prior to Baseline Visit.
- 15. Have open sores or open lesions in the treatment area(s).
- 16. Have a history of alcohol or illegal drug/substance abuse, or suspected alcohol or illegal drug/substance abuse in the past 2 years.
- 17. Require ≥ 2.0 mg/day inhaled or intranasal corticosteroids.
- 18. Have an active infection of any kind at Visit 1 Baseline.
- 19. Have an occupation that requires ≥50% of time be spent outdoors, where prolonged exposure to ultraviolet radiation is unavoidable.

4.4 SUBJECT ENROLLMENT

The Investigator will maintain a log of pre-screened subjects and an enrollment log of all subjects enrolled in the study indicating their assigned study number.

Each potential subject will sign and date an informed consent and a photography consent form before any study procedures are performed.

Once a potential subject is determined to be eligible for inclusion in the study, site personnel will conduct the study visit procedures and dispense study medication.

5. VISIT SCHEDULE AND ASSESSMENTS

5.1 STUDY PROCEDURES

The visit schedule and assessments are summarized in Table 5-1. A subject will have 5 visits: Screening Visit, Baseline Visit (Day 1), Treatment Visit 2 (Day 7), Treatment Visit 3 (Day 14), Telephone Call Visit 4 (Day 21) and a Final Visit 5 (Day 28) at the end of the study treatment. On Study Day 35, the subject will receive a follow-up phone call and be queried for condition status since going off study.

Confidential

San Antonio, TX Protocol No. SAN007-02 Final Am 6: 18-Sept-2017

Source documents will be completed at each subject's visit, and the data captured in the source documents will be subsequently entered into the electronic case report forms (eCRFs) by the Investigator or designee. In addition, two Telephone Visits, Visit 4 (Day 21 ± 2) and the Follow-Up (Day 35 ± 2) phone call will be conducted.

San Antonio, TX

Protocol No. SAN007-02 Final Am 6: 18-Sept.-2017

Table 5-1 Time and Events

Procedure	Screening Period Day-7 to 0	Treatment Period					Follow-Up
		Visit 1- Day 1	Visit 2- Day 7 (± 2 days)	Visit 3- Day 14 (± 2 days)	Visit 4- Day 21 (± 2 days)	Final Visit 5- Day 28 (± 2 days)	Follow-up Call- Day 35 (± 2 days)
Conduct informed consent and photography consent	x						
Record demographics	X						
Review inclusion/exclusion criteria	X	X					
Record/update all concomitant medications	x	X	х	x	X	х	
Perform a full physical examination	Х						
Record/update pertinent medical history ²	x	х	х	х	х	х	
Administer IGA and EASI	X	Х	X	X		X	
Calculate the BSA of treatment area	X	Х	Х	X		Х	
Tolerability Assessment		Х	X	X		X	
Perform an abbreviated physical examination ³		х					
If subject is female, collect urine sample and perform a β-human chorionic gonadotropin pregnancy test ⁴		х				х	
Weight study medication and record weights		х	х	x		х	
Calculate Expected Use per application		X					
Calculate Dose		X					
Calculate compliance			Х	X		X	
Dispense/re-dispense study drug ⁶		X					
Subject apply medication		X					
Instruct the subject on proper washing or the treatment area and self-application of study medication		х					
Photograph treatment area(s)		Х	Χ.	X		X	_
Instruct subject to return for next study visit		х	х		х		
Query for adverse events ⁷			X	X	Х	X	
Query for treatment regimen compliance			Х	Χ	Х	X	
Inform subject next contact will be by telephone				x		x	
Collect study medication						X	
Query for status of condition since study completion							х

Footnotes to Table 5-1: Time and Events

- 1- Site staff will follow the requirements of the IRB or Ethics Review Board to obtain informed consent from the Subjects
- 2- Only pertinent medical history will be recorded for each Subject

Confidential

San Antonio, TX

Protocol No. SAN007-02

Final Am 6: 18-Sept-2017

- 3- Only complete if Screening and Baseline visit are not done together
- 4- A urine pregnancy test will be completed for all subjects of child-bearing potential at the designated study visits, or at any visit if there is suspicion of pregnancy during the treatment period.
- 5- This should be done twice at Baseline Visit, before, and after application
- 6- Additional study drug may be dispensed at each visit depending on usage
- 7- Adverse events (AE) will be collected after the Subject's first treatment at Visit 1 and throughout the trial. Record only study medication related AE at Visit 5. If AE persists after the follow-up visit, the Subject may be required to return to assess the AE.

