6.1.6 EASI Total Score

The final EASI score is:

EASI= C1 + C2 + C3 + C4.

An increase in EASI score, from Baseline, during study participation, will be recorded as an AE. A new adverse event will be opened only if the PI assesses an increase in severity from initial AE. Otherwise, the initial adverse event will remain open until resolution or study completion.

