6.2 INVESTIGATOR GLOBAL ASSESSMENT

The Investigator Global Assessment (IGA) should be administered by the same Investigator, or designee, for any given Subject at all study visits. Any increase in IGA grade will be recorded as an AE. It will be used to measure efficacy according to the following scale:

Grade	Score	Description			
Clear	0	No inflammatory signs of AD			
Almost Clear	1	Just perceptible erythema and just perceptible population/infiltration			
Mild	2	Mild erythema and mild population/infiltration			
Moderate	3	Moderate erythema and moderate population/infiltration			
Severe	4	Severe erythema and severe population/infiltration			

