7.5 ADVERSE EVENTS

Information about all AEs, whether volunteered by the subject, discovered by investigator questioning, or detected through physical examination, or other means, will be collected and recorded on the Adverse Events page of the eCRF and followed as appropriate. Adverse events will be coded using an internationally recognized dictionary.

Medical conditions/diseases present before starting study treatment are only considered adverse events if they worsen after starting study treatment (i.e., any procedures specified in the protocol). Adverse events occurring before starting study treatment, but after signing the informed consent form, are recorded on the Medical History/Current Medical Conditions page of the eCRF.

As far as possible, each AE will also be described by:

- 1. its duration (start and end dates),
- 2. the severity grade (mild, moderate, severe)
- 3. its relationship to the study product (definitely, probably, possibly, unlikely, or not related),
- 4. the action(s) taken, and,
- 5. the outcome, as relevant.

Severity of adverse events

The investigator is to classify the severity of an AE according to the following definitions:

Mild: The Subject is aware of the signs or symptoms, which are easily

tolerated.

Moderate: The signs and symptoms are sufficient to restrict, but not prevent

usual activity.

Severe: The Subject is unable to perform usual activity.

The maximum intensity of an AE (mild, moderate, or severe) will be assessed considering the possible range of intensity of the symptom(s).

Relationship of adverse event to study treatment

The investigator is to classify the relationship of the AE to the investigational product according to the definitions outlined in Table 7-6.

The following study measurements will be reported as an AE:

- 1. Any increase in the subjects' EASI score or IGA during study participation.
- 2. A negative change in Tolerability, during or immediately after study drug application.

Table 7-6: Terms for Defining Relationship of Adverse Event to Study Product

Association	Definition	
Not related	(1) the existence of a clear alternative explanation (e.g., mechanical bleeding at surgical site) or (2) non-plausibility, e.g., the subject is struck by an automobile or develops cancer a few days after product administration.	

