Unlikely related	A clinical event, including laboratory test abnormality (if applicable), with an improbable time sequence to product administration and in which other drugs, chemicals for underlying disease provide plausible explanations.	
Possibly related	A clinical event, including laboratory test abnormality (if applicable), with a reasonable time sequence to administration of the drug, but which could also be explained by concurrent disease or other drugs or chemicals.	
Probably related	A clinical event, including laboratory test abnormality (if applicable), with a reasonable time sequence to administration of the drug, unlikely to be attributed to concurrent disease or other drugs or chemicals, and which follows a clinically reasonable response on withdrawal.	
Definitely related	A clinical event, including laboratory test abnormality (if applicable), with an established temporal or other association (e.g., re-challenge) and the event is not reasonably explained by the Subject's known clinical state or any other factor, based on available information.	

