7.1 Adverse Events

An adverse event (AE) means any untoward medical occurrence associated with the use of a drug in humans, whether or not considered drug related. An AE (also referred to as an adverse experience) can be any unfavorable and unintended sign (e.g., an abnormal laboratory finding), symptom, or disease temporally associated with the use of the drug, without judgment about causality. An adverse event can arise from any use of the drug (e.g., off-label use, use in combination with another drug) and from any route of administration, formulation, or dose, including an overdose. Non-serious AEs will be captured through the last treatment application, Day 28/exit, and serious AEs will be captured up through 28 days following the discontinuation of therapy.

All AEs reported will be considered to be treatment-emergent. Verbatim adverse events will be mapped to PT and SOC using MedDRA 19.0.

Tabular summaries of treatment-emergent adverse events (TEAEs) in terms of number of subjects will be presented by each study arm for the following:

- PT presented in order of descending incidence in the SAN007 group then alphabetically
- SOC and PT presented in order of descending incidence in SOC, then PT, in the SAN007 group, then alphabetically by SOC and PT
 - repeat presentation for subset of study-drug related events

• SOC, PT, and maximum severity grade (mild, moderate, severe) presented alphabetically by SOC and PT

Adverse events will be counted as treatment related if they are evaluated as possibly, probably, or definitely related to study treatment. Missing relationship will be treated as related. Subjects will be counted once within each level of summarization within each study arm for the calculation of incidence.

A summary of count and percent of subjects with at least one event in the following categories will be tabulated: any TEAE, any mild TEAE, any moderate TEAE, any severe TEAE, any treatment-related TEAE, any serious TEAE, any TEAE that led to discontinuation of study drug, and any deaths. Note that any AE is only considered for its maximum severity. However a subject can have more than one AE and each may have a different maximum severity. Thus severity levels are not mutually exclusive.

A comprehensive listing of all AEs will be provided by subject, which will include the duration of each event. Duration will be calculated as the stop date of the event minus the start date, unless the event is determined ongoing at exit.

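### Footnote 7 to Table 5-1 limits Visit 5 to drug-related AEs, against Section 7.5, so unrelated non-serious AEs first reported at that visit may be missing

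*Protocol*

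**What the plan says.** Table 5-1 of the protocol marks an AE query at Visits 2, 3, 4 and 5 and none at the Day 35 call. Its footnote 7 opens with a general rule: "Adverse events (AE) will be collected after the Subject's first treatment at Visit 1 and throughout the trial". The next sentence narrows it: "Record only study medication related AE at Visit 5". A third sentence deals with AEs that persist after a follow-up visit.

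The other rules on AE recording carry no such limit:

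- Protocol 7.5 covers "Information about all AEs, whether volunteered by the subject, discovered by investigator questioning" or found by other means, and sends it to the AE page of the eCRF. Its relationship scale includes unlikely and not related.
- Protocol 6.1.6: "An increase in EASI score, from Baseline, during study participation, will be recorded as an AE". Protocol 6.2: "Any increase in IGA grade will be recorded as an AE". Section 7.5 repeats both in its list of measurements to be reported: "Any increase in the subjects' EASI score or IGA during study participation".
- SAP 7.1 sets the window: "Non-serious AEs will be captured through the last treatment application, Day 28/exit, and serious AEs will be captured up through 28 days" after therapy stops. It counts possibly, probably and definitely related events as related, and treats a missing relationship as related.

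SAP 1.1.1 makes the number and percentage of subjects with at least one AE the measure for the primary objective.

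**The concern.** Under the footnote, the investigator's view of causality decides whether an event is recorded at all. Everywhere else in the plan it is an attribute of an event already recorded. An unrelated non-serious AE that first comes up at Visit 5 would be entered by a site working from Section 7.5 and left out by a site working from the footnote. The SAP's safeguard for a missing relationship cannot help, because it works only on events that are in the database.

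At stake are the all-cause summaries of the primary safety measure: SAP Tables 14.3.1.1, 14.3.1.2, 14.3.1.3 and 14.3.1.5. If events were left out, these may be too low and the related share of recorded AEs may look too high. Visit 5 is also the last AE query in Table 5-1, so no later scheduled query clearly picks up what was missed.

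**Working it through.** **1. The rules side by side**

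| Text | Bears on Visit 5? | Relatedness limit? | Fit with footnote 7 |
|---|---|---|---|
| Protocol 7.5, general rule | Yes, all AEs | None | Direct conflict |
| Footnote 7, first sentence | Yes, whole trial | None | Poor fit; could be read as rule plus exception |
| SAP 7.1 | Yes, through Day 28/exit | None | Poor fit; it sets a window and does not instruct sites |
| Protocol 6.1.6, 6.2 and the 7.5 measurement list | Yes, both scales are done at Visit 5 | None | Conflict only if the increase is judged unrelated |
| Protocol 5.2, Visit 5 steps | Yes, AE query | None | No contradiction; sets no recording rule |

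**2. Which events are exposed**

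- SAEs are not. Section 7.6 requires them to be reported from consent until four weeks after treatment.
- Related AEs are not, taking related in the SAP 7.1 sense. Table 14.3.1.4 therefore stands. The footnote itself does not define the term.
- EASI or IGA increases are exposed in part. Table 7-6 defines possibly related as an event "with a reasonable time sequence to administration of the drug, but which could also be explained by concurrent disease or other drugs or chemicals", and many increases could be placed there and so be recorded. Under Section 6.1.6, an EASI increase already open as an AE is not opened again unless its severity rises.
- What remains is non-serious events, judged unlikely or not related, that first surface at Visit 5.

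**3. Exposed interval** (visit days and ±2-day windows from Table 5-1)

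For queried AEs the last query before Visit 5 is the Visit 4 call:

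- nominal: 28 − 21 = 7 days; 7/(28 − 1) = 7/27 = 26% of the period from Day 1
- shortest: 26 − 23 = 3 days; 3/25 = 12%
- longest: 30 − 19 = 11 days; 11/29 = 38%

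EASI and IGA are not done at Visit 4, so an increase found at Visit 5 can date from Visit 3:

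- nominal: 28 − 14 = 14 days
- shortest: 26 − 16 = 10 days
- longest: 30 − 12 = 18 days

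**4. Size of the loss**

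The documents give no rate for unrelated AEs. Their only AE count is in Protocol 1.1: four subjects with probably or definitely related AEs beside 183 completers in a wart study (4/183 = 2.2%). That concerns related events in another indication.

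For illustration only, assume a constant hazard, nominal visit days, the footnote followed for every subject, and no event after Visit 4 reported before Visit 5. With true unrelated non-serious incidence I, recorded incidence = 1 − (1 − I)^(20/27), where 20 = 21 − 1 days to the last unrestricted query.

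| Assumed I | Recorded | Loss (points) |
|---|---|---|
| 5% | 1 − 0.95^(20/27) = 3.7% | 1.3 |
| 20% | 1 − 0.80^(20/27) = 15.2% | 4.8 |
| 40% | 1 − 0.60^(20/27) = 31.5% | 8.5 |

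At I = 20%, the visit windows move the recorded figure from 1 − 0.80^(18/29) = 12.9% to 1 − 0.80^(22/25) = 17.8%. The table uses the Visit 4 interval and so does not model EASI or IGA increases.

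**5. Effect on the any-AE summary**

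A subject drops out of the count only if the unrecorded event was that subject's only AE. Under the assumptions of step 4, each loss in the table is therefore an upper limit for the any-AE percentage.

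**The case against.** The strongest case for leaving this alone has four parts.

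*The limit was meant for post-treatment contact.* The footnote goes on to speak of a follow-up visit, and Section 5.2 brings subjects back after Visit 5 mainly for persisting study-related AEs. That reading is plausible, but it is an inference. The text names Visit 5 and needs correcting either way; it affects only whether the sentence is deleted or moved.

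*Sites would follow Section 7.5.* Some may have. Some events would also have reached the site before Visit 5, since Section 7.5 covers volunteered AEs and Section 7.1.4 tells subjects with a new or worsening rash to contact the site. This narrows the exposure without removing it.

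*The effect is small and the analysis descriptive.* This largely stands. It is why the point is one of repair and disclosure and does not threaten the trial's conclusions.

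*The planned 100% source check would catch it.* Not reliably. A monitor who finds an unrelated Visit 5 event in source but not in the eCRF could accept the footnote as the reason.

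Three stronger readings are tempting. A reader might infer that all-cause incidence is understated as a matter of fact. The documents do not show that any site followed the footnote or that any event was lost. A reader might infer bias between arms, because SAP 2.1 says some sites have only the 5%/placebo groups and some only the 10%/placebo groups. The rule is the same for all arms, and no difference in site practice is documented. A reader might also see a second contradiction at Day 35, where Protocol 5.2 lists only the status of atopic dermatitis and SAP 8.0 mentions safety data. Those words can mean the 28-day SAE follow-up, so this calls for clarification and is not a proven conflict.

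**Conclusion.** The conflict between footnote 7 and Section 7.5 is plain in the text, and confidence in it is high. The consequence is conditional. Where sites followed the footnote, unrelated non-serious AEs first reported at Visit 5 may be missing and the four all-cause TEAE tables may be too low. The any-AE count changes only for subjects with no other recorded AE.

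The exposed interval is 3 to 11 days for queried AEs and 10 to 18 days for EASI or IGA increases. The number of events lost cannot be derived. Losses of about 1.3 to 8.5 points in unrelated-AE incidence rest wholly on assumed incidences of 5% to 40%, a constant hazard and universal use of the footnote. The point should be fixed because it touches the primary measure and the correction is cheap.

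**What to change.** Reconcile footnote 7 with Section 7.5 and SAP 7.1 by removing the relatedness limit from Visit 5. If the limit was meant for contact after treatment, restate it there.

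The SAP is dated 11 October 2018 and the planned study end was January 2018, so the data are probably already collected. In that case:

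1. Check source documents for unrelated AEs noted at Visit 5 but not entered in the eCRF.
2. Compare Visit 5 EASI and IGA increases from baseline (Listings 16.2.6.5 and 16.2.6.4), and concomitant medications started after Visit 4 with their indications (Listing 16.2.8), with the AE listing (16.2.7).
3. Enter and code any events found.
4. State in the report that unrelated non-serious AEs first reported at Visit 5 may be incomplete. Wording it by when the event was reported also covers EASI and IGA increases that may date from Visit 3.

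Separately, say what safety data means in SAP 8.0 for the Day 35 call.

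The cost is one sentence changed in the protocol, one clarification in the SAP, a targeted source check, two listing comparisons, some data entry and coding, and one limitation sentence. No new table is needed. Events never written in source cannot be recovered, which is why the limitation sentence is needed whatever the checks find.
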